6.2 SUMMARIES OF CONDUCT OF STUDY

Patient enrollment, follow-up duration, study discontinuation, and discontinuation reasons will be summarized by treatment arm for all randomized patients. In addition, major protocol violations, including violations of inclusion and/or exclusion criteria, will be summarized by treatment arm. All of the analyses will be performed separately for patients with *PIK3CA*-mutant tumors and for patients without detectable *PIK3CA*-mutant tumors.

6.3 SUMMARIES OF TREATMENT GROUP COMPARABILITY

The evaluation of treatment group comparability between the two treatment arms will include demographics summaries, baseline disease characteristics (including *PIK3CA*-mutation status), and patient treatment history.

Descriptive summaries of continuous data will present the group mean, standard deviation, median, minimum, and maximum. Descriptive summaries of discrete data will present the category counts as frequencies and percentages.

All of the analyses will be performed separately for patients with *PIK3CA*-mutant tumors and for patients without detectable *PIK3CA*-mutant tumors.

6.4 EFFICACY ANALYSES

The primary efficacy analysis population will include all randomized patients with *PIK3CA*-mutant tumors. The primary efficacy endpoint, investigator-assessed PFS, and the secondary efficacy endpoints will be analyzed in this population as the primary and the secondary objectives.

In addition, these efficacy endpoints, unless otherwise specified, will be analyzed in all randomized patients without detectable *PIK3CA*-mutant tumors at the same time as the analyses are conducted for the patients with *PIK3CA*-mutant tumors.

PIK3CA-mutant tumor status will be determined by the cobas *PIK3CA* mutation test of the patient's tissue sample.

The treatment arm assigned at randomization will be used for all efficacy analyses.

6.4.1 Primary Efficacy Endpoint

The primary efficacy endpoint is investigator-assessed PFS (PFS in this document refers to investigator-assessed PFS, unless stated otherwise). The primary PFS analysis will be conducted in all randomized patients with *PIK3CA*-mutant tumors, with patients grouped according to the treatment arm assigned at randomization.

An interim efficacy analysis will be conducted for investigator-assessed PFS at the time of 172 investigator-assessed PFS events (expected 21 months after the first patient is enrolled), and the final efficacy analysis will be conducted at the time

287 investigator-assessed PFS events (expected 29 months after the first patient is enrolled) are observed in patients with *PIK3CA*-mutant tumors. The α -spending function is specified as Gamma (-16), which allocates two-sided $\alpha = 1.7 \times 10^{-5}$ at the interim efficacy analysis of investigator-assessed PFS, when 172 PFS events have occurred and preserves the two-sided 1% α -level at the final PFS analysis. The exact boundary will be calculated on the basis of the exact number of PFS events observed at the interim analysis. The associated minimal detectable difference for the investigator-assessed PFS hazard ratio at the interim efficacy analysis is 0.5 (i.e., 100% improvement in median investigator-assessed PFS from 4.5 months in the control arm to 9 months in the treatment arm). Refer to Section 6.9.1 for additional details on the interim analysis.

Table 11 PFS Analyses

	Estimated Timing (Clinical Data Cutoff)	PFS Events	Two-Sided p-Value Boundary	Rejection HR Boundary ^a	Percentage Information
PFS IA	~21 months after FPI	~172	1.7×10^{-5}	0.5	60%
PFS FA	~29 months after FPI	~287	0.01	0.72	100%

IA=interim analysis; FA=final analysis; FPI=first patient in; HR=hazard ratio;
PFS=progression-free survival.

^a Assuming exponential distributions for the PFS event time of the two treatment arms.

An exploratory analysis for investigator-assessed PFS will also be conducted in all randomized patients without detectable *PIK3CA*-mutant tumors at the time of the primary PFS analysis in all randomized patients with *PIK3CA*-mutant tumors.

Data for patients without the occurrence of disease progression or death as of the clinical data cutoff date will be censored at the time of the last tumor assessment (or at the time of randomization if no tumor assessment was performed after the baseline visit).

The two-sided log-rank test stratified by the three stratification factors will be used as the primary analysis to compare investigator-assessed PFS between the two treatment arms. The three stratification factors are: 1) visceral versus non-visceral, 2) sensitivity versus non-sensitivity to their most recently administered endocrine therapy, and 3) geographical regions (details in, Section 3.1). The Kaplan-Meier approach will be used to estimate median investigator-assessed PFS for each treatment arm. Cox proportional-hazards models stratified by the three stratification factors will be used to estimate the HR and its 95% CI. The results from the unstratified log-rank test will also be provided.

6.4.2 Secondary Efficacy Endpoints

Assuming that the primary endpoint PFS is statistically significant, the first two secondary endpoints are planned to be tested in the following hierarchical order:

- Overall ORR
- OS

6.4.2.1 Overall Objective Response Rate

The analysis of ORR will include only patients who have measurable disease per RECIST v1.1 at baseline as a secondary endpoint of the study and will be tested on the basis of a hierarchical testing procedure to preserve the type I error. That is, the ORR analysis will be conducted at the significance level of two-sided 5% at the time that a statistically significant benefit is observed for the investigator-assessed PFS at either the interim efficacy or final PFS analysis.

An estimate of the response rate and its 95% CI will be calculated using the Blyth-Still-Casella method for each treatment arm. Response rates in the treatment arms will be compared using the stratified Mantel-Haenszel test. Confidence intervals for the difference in ORRs between the two arms will be determined using the normal approximation to the binomial distribution.

6.4.2.2 Overall Survival

The analyses for OS will be conducted in all randomized patients with *PIK3CA*-mutant tumors as a secondary endpoint of the study and will be tested on the basis of a hierarchical testing procedure to preserve type I error. That is, the OS analysis will be tested only if both investigator-assessed PFS and ORR have reached their respective significance levels. The overall type I error for OS is preserved at two-sided 5%.

OS will be analyzed with patients grouped according to the treatment arm assigned at randomization. Data for patients who are alive at the time of the analysis data cutoff will be censored at the last date they were known to be alive. Data from patients without post-baseline information will be censored at the date of randomization.

The analyses will be conducted using the stratified two-sided log-rank test, and the results from the unstratified log-rank test will also be provided. The OS curve for each treatment arm will be estimated by the Kaplan-Meier methodology, and the HR and its 95% CI will be estimated by the Cox proportional-hazards models.

Three interim analyses and one final analysis for OS *were originally* planned in patients with *PIK3CA*-mutant tumors on the basis of the results from the cobas *PIK3CA* mutation test (see [Table 12](#) and [Table 13](#)). *As a result of the completion of the primary PFS analysis, the Sponsor has decided to limit the additional OS follow-up to one additional analysis. This additional OS analysis coincides with the originally planned second OS interim analysis.*

1. The first interim OS analysis will be conducted at the time when both investigator-assessed PFS and ORR have reached their respective significance levels, so it could occur at the time of the interim efficacy or the final efficacy analysis for investigator-assessed PFS.
2. The second OS analysis will be conducted approximately 10 months after the first interim analysis.

Table 12 Analyses for OS if the First Interim OS Analysis Occurs at the Time of the Interim Efficacy Analysis of Investigator-Assessed PFS

	Estimated Timing (Clinical Data Cutoff)	OS Events	Two-Sided p-Value Boundary	Rejection HR Boundary ^a	Percentage Information
First OS IA	~21 months after FPI	~63	0.001	0.44	19%
Second OS analysis	~10 months after first OS IA	~134	0.010	0.65	41%

IA=interim analysis; FPI=first patient in; HR=hazard ratio; OS=overall survival; PFS=progression-free survival.

^a Assuming exponential distributions for the OS event time of the two treatment arms.

Table 13 Analyses for OS if the First Interim OS Analysis Occurs at the Time of the Final Efficacy Analysis of Investigator-Assessed PFS

	Estimated Timing (Clinical Data Cutoff)	OS Events	Two-Sided p-Value Boundary	Rejection HR Boundary ^a	Percentage Information
First OS IA	~29 months after FPI	~118	0.001	0.53	36%
Second OS analysis	~10 months after first OS IA	~188	0.010	0.67	57%

IA=interim analysis; FPI=first patient in; HR=hazard ratio; PFS=progression-free survival.

^a Assuming exponential distributions for the OS event time of the two treatment arms.

The stopping boundaries are computed using the generalized Haybittle-Peto boundaries with unequal p-values being used in the α -spending function and will be adjusted on the basis of the actual number of OS events observed at each interim OS analysis.

The timing of the analyses are based on an assumption of an annual loss-to-follow-up rate of 5%. The study team will be unblinded at the time when the iDMC recommends to stop the study and the Sponsor decides to stop the study, or at the time of the final PFS analysis if the study is not stopped early. Investigators and patients will remain blinded to individual patient-level treatment assignment until *approximately the end of August 2018, at which time unblinding is permitted at the discretion of the investigator or Sponsor.*

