4.2 METHOD OF TREATMENT ASSIGNMENT AND BLINDING

After written informed consent has been obtained and eligibility has been established and approved, the study site will obtain the patient's identification number and treatment assignment from the interactive voice/Web response system (IxRS). Patients will be randomized to receive either taselisib + fulvestrant or the placebo + fulvestrant on the basis of a 2:1 randomization ratio. Patients with *PIK3CA*-mutant tumors and patients without detectable *PIK3CA*-mutant tumors will be randomized separately using a permuted-block randomization method.

Randomization will be stratified by the following criteria:

- Visceral versus non-visceral disease
 - Visceral disease: Metastatic disease in the lung, liver, adrenal glands, brain, heart, pericardium, pleura, peritoneum, or other end-organs of the chest, abdomen, and pelvis
 - Non-visceral disease: Absence of metastatic disease in visceral organs. Pleural effusions, ascites, disease involving lymph nodes, and disease involving bone are not considered to be visceral disease.

- Sensitivity versus non-sensitivity to the patient's most recently administered endocrine therapy
 - Sensitive to most recently administered endocrine therapy (fulfilling either of the criteria below):
 - For patients with no endocrine treatment in the advanced or metastatic setting, at least 24 months of adjuvant endocrine therapy prior to disease recurrence
 - Documented clinical benefit (CR, PR, or SD \geq 24 weeks) to most recent endocrine treatment in the advanced or metastatic treatment setting
 - Non-sensitive: not satisfying criteria listed as sensitive
- Geographical region:
 - Western Europe, United States, Canada, Australia
 - Asia
 - Rest of World (remaining countries)

The iDMC, the independent statistical group (an independent vendor) facilitating the iDMC meetings, and the Sponsor-independent PK bioanalytical personnel will be unblinded to the treatment assignment. The study team will be unblinded at the time when the iDMC recommends to stop the trial and the Sponsor decides to stop the trial or at the time of the final PFS analysis if the study is not stopped early. Investigators and patients will remain blinded to individual patient-level treatment assignment until *approximately the end of August 2018, at which time unblinding is permitted at the discretion of the investigator or Sponsor.*

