6. STATISTICAL CONSIDERATIONS AND ANALYSIS PLAN

6.1 DETERMINATION OF SAMPLE SIZE

The global study plans to enroll approximately 600 patients, including 480 patients with detectable *PIK3CA*-mutant tumors, and 120 patients without detectable *PIK3CA*-mutant tumors (tumor status determined by the cobas *PIK3CA* mutation test).

After the global enrollment closes, additional Chinese patients may continue to be recruited into the China extension cohort. A total of up to 150 patients with detectable *PIK3CA*-mutant tumors may be enrolled as part of the global study population and the China extension cohort combined (see Section 6.10 for further details).

The sample size of 480 patients with *PIK3CA*-mutant tumors is determined on the basis of the power calculation for the PFS and the OS endpoints, whichever requires a larger sample size. In this case, the sample size is driven by OS.

In 480 patients with *PIK3CA*-mutant tumors, approximately 287 investigator-assessed PFS events will be required to detect a hazard ratio of 0.59 in PFS (3.1 months of

improvement in median PFS) with 95% power at the a two-sided significance level of 1%, assuming a median PFS of 4.5 months in the control arm (Mauriac et al. 2009; Johnston et al. 2013). One interim efficacy analysis of investigator-assessed PFS will be conducted at 60% of PFS information (see Section 6.9.1 for more details). The α -spending function specified as Gamma (-16), which allocates two-sided $\alpha = 1.7 \times 10^{-5}$ at the interim efficacy analysis of investigator-assessed PFS, when 172 investigator-assessed PFS events have occurred. The minimal detectable difference for investigator-assessed PFS hazard ratio at final PFS analysis is 0.72 (i.e., 39% improvement in median investigator-assessed PFS from 4.5 months in the control arm compared with 6.2 months in the treatment arm), when 287 investigator-assessed PFS events have occurred.

With the aforementioned sample size of 480 patients with *PIK3CA*-mutant tumors, the OS analyses in this population will require 330 deaths to detect an hazard ratio of 0.7 in OS (11.1 months of improvement in median OS) with 80% power at a two-sided significance level of 5%, assuming a median OS of 26 months in the control arm based on the OS of 26.4 months in patients treated with 500 mg fulvestrant in the CONFIRM study, which investigated 500 mg fulvestrant versus 250 mg fulvestrant in a similar patient population (Di Leo et al. 2014).

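### Protocol version 4 still states a two-sided 5% level for OS, but the two OS looks it keeps form a test at about 1.04%, and the unspent alpha is not accounted for

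*Combined protocol and SAP*

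**What the plan says.** Protocol Section 6.4.2.2 says of the OS hierarchy that "The overall type I error for OS is preserved at two-sided 5" percent. Section 6.1 sizes OS on the same level: "the OS analyses in this population will require 330 deaths to detect an hazard ratio of 0.7 in OS", with "80% power at a two-sided significance level of 5" percent. The protocol synopsis repeats this.

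Version 4 then shortens the OS plan. Section 6.4.2.2 records that "the Sponsor has decided to limit the additional OS follow-up to one additional analysis" and that "This additional OS analysis coincides with the originally planned second OS interim analysis". Tables 12 and 13 now hold two rows each. Table 13 lists about 118 deaths at p 0.001 and about 188 deaths at p 0.010. On the boundaries, the section says: "The stopping boundaries are computed using the generalized Haybittle-Peto boundaries". It allows them to be adjusted for the number of OS events actually observed. Section 6.9.1 refers back to 6.4.2.2 for the decision boundary at each OS analysis.

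SAP version 2, signed in March 2017 before this amendment, still has four OS looks. Its Table 3 adds a third interim at 232 deaths (p 0.045) and a final analysis at 330 deaths (p 0.013).

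**The concern.** The 5% appears to have been carried over from a design that version 4 no longer contains. Removing the third interim and the final analysis removes the looks at which most of the alpha was to be spent, yet the level was not restated. The information percentages in Table 13 show the same carry-over: 118/330 = 36% and 188/330 = 57%, both measured against a death count that is no longer pursued.

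What is at stake is the description of the OS test. Anyone who takes the OS level from 6.1 or 6.4.2.2 will believe that the trial tests OS at 5% overall, when its two boundaries amount to about a 1% test. The protocol also does not say whether the remaining alpha is given up. The only adjustment rule covers event counts, not dropped looks. Under both 4.2 and 6.4.2.2 the study team is unblinded from the final PFS analysis, so the point is better settled in writing than left to interpretation.

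**Working it through.** **Which table applies.** The amendment rationale reports p = 0.0037 for the primary PFS analysis. That is above the interim boundary of 1.7 × 10⁻⁵ and below the final boundary of 0.01 (Table 11). The first OS look therefore falls at the final PFS analysis, which is the Table 13 scenario. The PFS data cutoff was 15 October 2017 (Section 4.5.5). Ten months later is mid-August 2018, which fits the end of survival follow-up around the end of August 2018. The second OS look is thus the last.

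**Inputs.** 118 and 188 deaths, nominal two-sided p 0.001 and 0.010 (Table 13); allocation "on the basis of a 2:1 randomization ratio" (Section 4.2), so the information is D × (2/3) × (1/3) = D × 2/9; design OS hazard ratio 0.70 (Section 6.1).

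**The tabulated boundaries reproduce.** HR boundary = exp(−z / √(2D/9)).
- 118 deaths, z = 3.291: exp(−3.291/5.121) = 0.526 (stated 0.53).
- 188 deaths, z = 2.576: exp(−2.576/6.464) = 0.671 (stated 0.67).

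**The stated 5% reproduces for four looks.** The crossing probability under no effect was obtained by recursive numerical integration of the log-rank score process, with independent increments and information proportional to deaths. Cumulative two-sided alpha for SAP Table 3:

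| Deaths | Nominal p | Cumulative alpha |
|---|---|---|
| 118 | 0.001 | 0.0010 |
| 188 | 0.010 | 0.0104 |
| 232 | 0.045 | 0.0463 |
| 330 | 0.013 | 0.0500 |

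Power at HR 0.70 for these four looks is 79.3%, close to the stated 80%. The 5%, the 330 deaths and the 80% all belong to this plan.

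**The two retained looks.** Overall alpha = P(|Z₁| ≥ 3.291) + P(|Z₁| < 3.291 and |Z₂| ≥ 2.576), with correlation √(118/188) = 0.79.
- First look: 0.00100.
- Added at the second look: 0.00936.
- Total: 0.01036, or 1.04%.

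A check by hand: the total cannot be below the larger nominal level, 0.010, or above the sum, 0.001 + 0.010 = 0.011. Any correct method must give between 1.0% and 1.1%.

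**Unassigned alpha.** 5.00% − 1.04% = 3.96 percentage points, which is 3.96/5.00 = 79% of the stated level.

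**Power of the retained test at HR 0.70.** At 188 deaths the expected z is 0.3567 × 6.464 = 2.305. A single look at p 0.010 has power Φ(2.305 − 2.576) = 39%. Including the first look gives 39.6%, or about 40%.

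**The case against.** The strongest reply is that no stated figure is false. Preserving type I error at 5% is a statement of control, and a procedure that spends 1.04% satisfies it. Giving up alpha when follow-up is shortened is a legitimate, conservative choice. It also avoids any appearance of relaxing the OS criterion after the sponsor was unblinded. All of this stands. The concern is neither inflation nor the choice of 0.010.

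A reader might infer something stronger: that an OS p-value between 0.010 and about 0.05 is negative by Table 13 but positive under the stated 5%, so that observed hazard ratios of about 0.67 to 0.74 would be decided in two ways. The documents do not support that. An overall alpha across looks is not a nominal threshold at one look. Section 6.9.1 sends the reader to 6.4.2.2 for the boundary, and Table 13 gives 0.010 for the last look. The second interim with which this look coincides also has 0.010 in the SAP. The upper limits (p of about 0.0499, HR 0.74) arise only if the unspent alpha is moved to the last look, and no section says that it is.

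It may also be said that the SAP declares that it overrides the protocol's statistical section and still has four looks totalling 5%. But that SAP predates version 4, and version 4 ends survival follow-up around the end of August 2018, so the looks at 232 and 330 deaths cannot take place as planned.

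Finally, OS is formally tested only if ORR as well as PFS is significant, and the documents give no ORR result. The practical effect is therefore conditional.

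**Conclusion.** The point holds as a misstated level, not as a loss of error control. The OS test in version 4 has an overall two-sided type I error of about 1.04%, against a stated 5% that belonged to the SAP's four looks. The fate of the remaining 3.96 percentage points is not stated. At the design hazard ratio of 0.70 the retained boundaries have about 40% power, whereas Section 6.1 still quotes 80% with 330 deaths. Read literally, the last-look decision rule is unambiguous at p 0.010.

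This rests on Table 13 being the live scenario, on death counts near 118 and 188, and on the usual independent-increments behaviour of the log-rank statistic. The alpha is insensitive to the last two, because it must lie between 1.0% and 1.1% for any pair of looks at these nominal levels. The power depends directly on the number of deaths.

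**What to change.** In Section 6.4.2.2, replace the 5% sentence with a statement that, with OS limited to two analyses, the boundary at the last analysis remains p 0.010, the overall two-sided type I error for OS is about 1%, and the unspent alpha is not carried forward. Restate the OS level in Section 6.1 and in the synopsis to match, making clear that 330 deaths and 80% power at 5% describe the original four-look plan. Align the OS section of the SAP, which still lists four looks. Do this before the last OS analysis.

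The cost is a few sentences in the protocol and a matching SAP update. No boundary, data collection or analysis method changes, and the edit cannot inflate error. The downside is a less favourable stated alpha, about 1% instead of 5%, and a written commitment not to use the remainder.

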6.4.2.3 Clinical Benefit Rate

The analysis of CBR will be performed for patients with PIK3CA-mutant tumors with measurable disease per RECIST v1.1 at baseline and will be repeated for the group of patients with PIK3CA-mutant tumors regardless of measurable disease at baseline. An estimate of CBR and its 95% confidence interval will be calculated using the Blyth-Still-Casella method for each treatment arm. The clinical benefit rates in the treatment groups will be compared using the stratified Mantel-Haenszel test. Confidence intervals for the difference in clinical benefit rates between the two arms will be determined using the normal approximation to the binomial distribution.

6.4.2.4 Duration of Objective Response

The analysis of DOR will include only patients who achieved an objective response to study treatment, among patients with measurable disease per RECIST v1.1 at baseline.

DOR will be estimated using the Kaplan-Meier methodology, with patients grouped according to the treatment arm assigned at randomization. Comparisons between treatment arms using stratified and unstratified log rank test will be made for descriptive purposes. Because the determination of DOR is based on a nonrandomized subset of patients, formal hypothesis testing will not be performed.

